2.2 Aims and Hypotheses

The proposed trial will determine the feasibility of an at-home resistance training protocol and measurements of exercise logging, functional fitness testing, DXA, dried blood spots and questionnaire measures. Participants will be assigned either to the resistance training program (i.e., initial in-person instructional session, telephone coaching, and self-monitoring) or to a comparison arm (wait-list control).

- **Aim 1:** To determine the feasibility of recruiting and retaining endometrial cancer survivors to a home-based resistance training 2 sessions per week of 20-40 minutes of exercise. *We hypothesize that we will meet the accrual goal and maintain >90% retention.*
- **Aim 2:** To determine participant satisfaction with each component of the intervention and identify opportunities for refinement of the intervention prior to testing in a larger study. *We hypothesize that the participants will adhere to 90% of the prescribed exercise sessions and that overall satisfaction will be high.*
- **Aim 3:** To establish that functional and objective assessments are feasible and well-tolerated in enrolled participants, as assessed using the functional fitness test (FFT) battery, dual-energy x-ray absorptiometry (DXA), finger-pricks for dried blood spots and patient-reported outcomes. *We hypothesize that these assessments will be well tolerated, as measured by the percent of participants who complete all measures and data from participant feedback questionnaires.*

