4.1 General Design

- A phase III, randomized, two-arm trial with a wait-list control group
- The intervention itself is 10 weeks, with an additional five week follow up assessment for those in the exercise arm to determine adoption of the program. Overall, the anticipated total duration should be 20 weeks for participants
- The intervention will consist of (a) an initial in-person instructional session; (b) instructional materials and resistance training equipment (e.g., resistance bands) and (c) support and feedback provided via video coaching sessions; and (d) a final in-person study visit to collect post-study measures for both groups

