Table 2. Series of exercises, with progressions and regressions to increase/decrease difficulty.

Primary muscle group	Exercise	Progressions	Regressions
Thighs (quadriceps, hamstrings)	Body weight squats	
• Add resistance band• Holding dumbbells	
• Chair squats• Shortened range of motion
Calves (gastrocnemius, soleus)	Standing heel raises	
• Holding dumbbells• Elevate ball of foot	
• Shortened range of motion
Chest (pectoralis major & minor)	Standing chest press	
• Increase band tension	
• Reduce band tension
Back (trapezius, latissimus dorsi)	Seated banded row	
• Standing row• Increase band tension	
• Reduce band tension• Shorten range of motion
Abdominals (rectus & transversus abdominus)	Static v-sit hold with feet on floor	
• Elevate feet• Add rotation• Add dumbbell	
• Support with hands• Add lumbar support w/ towel
Shoulders (deltoids)	Seated banded press	
• Standing• Use dumbbells	
• Reduce band tension• Shorten range of motion
Biceps brachii	Seated banded curl	
• Standing• Add tension to band• Use dumbbells	
• Reduce band tension• Shorten range of motion
Triceps brachii	Seated arm extension	
• Increase band tension	
• Reduce band tension

During the study period, participants in the intervention arm will be instructed to complete the exercise routine twice a week for 10 weeks during the intervention, and also continued throughout the five week follow up period. There are eight video calls with the study coordinator to check in, to identify any issues or concerns with the exercises, and to finally monitor progress in the form of assessing volume/intensity/difficulty of each of the exercises. These calls are done over video so that the coordinator can build rapport with participants, and that participants can show

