or demonstrate issues with exercises or their form. At the mid-point of the study, participants will receive an email with the questionnaires, so that the questionnaires will be done at baseline, at the study mid-point, and at the final visit.

Participants in the intervention group will also complete accelerometer (Actigraph) assessments at three study points: Early in the intervention near the instructional visit, at the mid-way (5-week) mark, and before the final visit. These accelerometers will be sent and received via mail and participants will receive instructions on how to wear, use and send to us during the instructional visit.

At the end of the 10 week period, participants will return to the UW campus for a final visit to repeat baseline study measures. At this time, intervention arm participants will also complete an exit-style interview with the study coordinator to help improve the intervention for future participants. This will be recorded, but anonymized upon transcription.

While the formal intervention period will be 10 weeks in duration, we will continue to follow those in the exercise arm for five weeks post-final assessment. This follow up period will consist of surveys to the participants assessing the frequency of the home-based resistance exercise, to determine if the behavior of exercise persists in the short-term following intervention conclusion.

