 - **When collected:** Baseline, mid-point (~5 weeks), final visit (~10 weeks)
- **Self-efficacy.** This will be assessed using the validated self-efficacy for exercise scale, modified for specificity to strength training.³⁴ These measures will be repeated at the study mid-point (5 weeks) to assess changes over time.
 - **When collected:** Baseline, mid-point (~5 weeks), final visit (~10 weeks)
- **Adherence.** Compliance and adherence will be measured via detailed exercise logs. A participant needs to complete at least 50% of the prescribed exercises in a session to be considered adherent to the session.
 - **When collected:** ongoing, logs will be completed throughout the intervention and submitted at the final visit
 - Additionally, for those in the intervention arm, we will ask that they continue to conduct the prescribed exercises for an additional five weeks after study completion. Participants will still submit paper logs, and this adherence measure will allow for study of adherence without prescribed check-ins from the study coordinator over the five week period.
- **Acceptability.** Participants will participate in a semi-structured qualitative interviews with the study coordinator. Interviews will be recorded, transcribed and coded to identify content themes. These interviews will be used to collect qualitative information and overall satisfaction with the intervention, as well as areas to improve with future interventions and barriers to participation.
 - **When collected:** Final visit (~10 weeks)

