8.2 Video calls

Participants will receive a tablet for the duration of the intervention for video conferencing with research team. Phone call conferencing will be available, however the tablets allow for video applications so that participants can visually interface with members of the research team. Additionally, using video conferencing allows participants to receive feedback and form recommendations from her home if she has questions or would like feedback on her performance for specific exercises. However, because this is a pilot intervention, we aim to determine if the video

conferencing component is useful. By providing each participant with a tablet, we are inclusive for individuals who may not have access to these resources on her own. Each participant will receive a check-in at eight points during the 10 week study: two calls in the first week, one during weeks three four and five, one during week six , and finally one during week eight consistent with their preferred contact method to provide feedback on their progress and resistance training. The study coordinator will ask about overall qualitative satisfaction, and issues the participant is having, and any questions that the study coordinator could potentially address. Participants are welcome to reach out to the lab or study coordinator at any point during the study, however these pre-planned check in visits will hopefully facilitate discussion if any issues remain unaddressed.

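### Weeks 11-15 are said to show adoption and persistence of exercise, but the prescription continues, so they show short-term adherence without scheduled check-ins

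*Combined protocol and SAP*

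**What the plan says.** The protocol gives the five-week follow-up of the exercise arm two descriptions.

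**As a measure of what happens after the program.** Section 4.1 (General Design) calls it an "additional five week follow up assessment for those in the exercise arm to determine adoption of the program". Section 8 (Study Procedures, Exercise interventions) says it will consist of "surveys to the participants assessing the frequency of the home-based resistance exercise", and gives the purpose as "to determine if the behavior of exercise persists in the short-term following intervention conclusion".

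**As a continuation of the prescription.** The same part of Section 8 says exercise-arm women will be instructed to complete the routine "twice a week for 10 weeks during the intervention, and also continued throughout the five week follow up period". Section 8.1 (Measures, Adherence) says "we will ask that they continue to conduct the prescribed exercises for an additional five weeks after study completion". It adds: "Participants will still submit paper logs, and this adherence measure will allow for study of adherence without prescribed check-ins from the study coordinator".

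The wait-list arm has no corresponding follow-up (Section 8, Wait list interventions). Table 3 also marks device-measured activity, satisfaction and safety at 15 weeks.

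**The concern.** Adoption, and persistence after an intervention has concluded, are naturally read as statements about what women do when the study no longer asks them to exercise. Here the study is still asking. A woman who trains twice a week in week 13 may have taken up the habit, or she may be doing what she was told to do and record. The planned data cannot separate the two.

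What is at stake is one conclusion. If the plan is followed as written, a high session frequency in weeks 11-15 meets the stated purpose and would naturally be reported as women keeping up strength training after the program ended. This pilot is meant to inform a larger study (Sections 2.1 and 2.2), whose designers could then assume a durability that was never observed.

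**Working it through.** The protocol states no figure to reproduce, and the sample size of 40 has no formula behind it. The check compares the sections, with a count of sessions.

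**Step 1. What is in force in weeks 11-15.**

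| Feature | Weeks 1-10 | Weeks 11-15 | Source |
|---|---|---|---|
| Twice-weekly routine instructed or requested | yes | yes | Sections 8, 8.1 |
| Logs submitted | yes | yes | Section 8.1 |
| Scheduled coordinator check-ins | yes, on set dates | no | Sections 8.1, 8.2 |
| Survey of exercise frequency | not described | yes | Section 8 |
| Wait-list arm followed | yes | no | Section 8 |

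**Step 2. Session counts.**

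- Weeks 1-10: 2 sessions x 10 weeks = 20 sessions.
- Weeks 11-15: 2 sessions x 5 weeks = 10 sessions.
- Total under instruction: 20 + 10 = 30 sessions.
- Follow-up weeks in which the instruction applies: 5 of 5.
- Women contributing: about 40 x 1/2 = 20 under 1:1 allocation, before any losses.

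**Step 3. What each follow-up instrument can measure.**

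- *Logs.* They record sessions done against a prescription that still applies. That is adherence.
- *Frequency surveys.* These are a separate instrument, but the same women answer them about the same weeks under the same instruction. A second instrument does not change the condition being observed.
- *Device measure at 15 weeks (Table 3).* It is taken under the same instruction. Section 8.1 also assigns the accelerometer to aerobic and lifestyle activity, not to resistance sessions.

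**Step 4. Compare with the stated purposes.** Exercise after the prescription has ended needs at least some observation time without the prescription. The plan has none. Adherence without scheduled check-ins needs the prescription to continue while the check-ins do not. The plan provides that, and Section 8.1 says so. The instruments therefore fit the purpose in Section 8.1 and not the broader wording in Section 4.1 and in the follow-up paragraph of Section 8.

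**Step 5. Effect on the main adherence result.** With a denominator of 20 sessions, the 10-week estimate is untouched. Section 9.3.1 compares completed with prescribed sessions without stating the window. Ten weeks is the natural reading, but because the instruction runs to week 15, a count of 30 could be taken from the text. Reporting the two periods separately removes that ambiguity.

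**The case against.** The strongest defence is that Section 8.1 already states what these weeks deliver, so the other two sentences are only looser wording. The protocol defines neither adoption nor persistence as uninstructed exercise; a program can be adopted along with its routine and its logs, and Section 8.1 words the continuation as a request. Section 8 also defines the formal intervention as 10 weeks, so persistence could simply mean persistence after coaching. No decision rule, aim or specified analysis depends on it.

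Much of this stands, and it is why the point is minor. It does not remove the point. Reading persistence as continuation after coaching gives exactly the quantity in Section 8.1, which concedes that the objective should say so. A request to continue the prescribed exercises is still a request from the study.

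A reader might go further in three ways that the documents do not support.

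- *Coaching is the only thing that changes after week 10.* It is not. The tablet is provided for the intervention period (Section 8.2), the second payment is made at the 10-week visit (Section 7.6.6), and that visit and its interview are over (Section 8). Weeks 11-15 against weeks 1-10 is therefore not a clean contrast of coaching with no coaching.
- *A named intervention component is still being delivered through the logs.* Section 2.2 does describe the program as "initial in-person instructional session, telephone coaching, and self-monitoring". But the component lists in Sections 2.1 and 4.1 omit self-monitoring, and Section 8.1 treats the logs as a measure. The point rests on the continued instruction, which is enough alone.
- *Weeks 9-10 already reproduce the follow-up conditions*, since Section 8.2 lists its calls in order "and finally one during week eight consistent with their preferred contact method". Those weeks lead up to a paid in-person visit at which logs are handed in. No such visit or payment is described after weeks 11-15, so the two periods are not equivalent.

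**Conclusion.** The concern holds as a mismatch between the stated objective and what is observed. Surveys and logs in weeks 11-15 estimate short-term adherence to a continued prescription without scheduled coordinator check-ins. They do not estimate exercise once the prescription has ended.

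Severity is minor. It affects the interpretation of one descriptive outcome in about 20 women, and the follow-up appears in no aim or hypothesis (Section 2.2) and in no listed endpoint (Sections 4.1.1 and 4.1.2).

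A reader might infer that the follow-up will overstate persistence by some definite amount. The documents give no rate of uninstructed exercise, so the size of any gap is unknown, and it could be small. What can be said is that the design cannot reveal it.

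The conclusion assumes that the instruction in Section 8 and the request in Section 8.1 are actually given. The statement that the 10-week estimate is unaffected assumes a denominator of 20 sessions.

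**What to change.** Restate the follow-up objective in Section 4.1 and in the follow-up paragraph of Section 8 as short-term adherence to the continued prescription without scheduled check-ins, in line with Section 8.1. Limit any conclusion from the weeks 11-15 surveys and logs to that quantity. Report it separately from the weeks 1-10 adherence estimate, and state in Section 9.3.1 that the latter uses 20 prescribed sessions.

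The cost is a few sentences of protocol text and care in reporting; visits, instruments and participant burden stay the same. The price is a more modest claim: the trial would not speak to adoption, or to exercise after the prescription has ended.

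If the investigators do want that stronger claim, they would have to end the instruction and the logs at week 10 and ask about exercise in the week-15 survey. That changes conduct and gives up the adherence measure now planned, so rewording is the proportionate choice.

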8.1 Measures

Below are the study measures that will be collected over the course of the intervention:

- Demographics and other participant characteristics: Participants will self-report age, race/ethnicity, marital status, education, and cancer characteristics (tumor type and stage, dates of diagnosis and treatment completion, treatment received). Clinical information will be confirmed with the medical record.
 - **When collected:** Baseline
- Accelerometer. Although aerobic and lifestyle PA (e.g., MVPA, steps) are not a focus of the intervention, they will be assessed to determine baseline PA level and identify whether uptake of resistance training is associated with changes in other PA types. Participants will wear the ActiGraph wGT3X-BT accelerometer (ActiGraph, Pensacola, FL) for 7 days during all waking hours. The ActiGraph is a gold standard method of objective activity assessment.^{26,27}
 - **When collected:** Baseline, mid-point (~5 weeks), final visit (~10 weeks)
- Biomarkers. Using a standardized protocol, participants will undergo a fingerstick to collect a peripheral blood sample to assess glycosylated hemoglobin (A1c) and c-Reactive Protein²⁸ via dried blood spots. The values for both A1c and CRP are highly correlated between dried blood spots and venipuncture.²⁹
 - **When collected:** Baseline, final visit (~10 weeks)
- Anthropometrics. Height, weight, waist and hip circumferences will be measured according to standard protocols.
 - **When collected:** Baseline, final visit (~10 weeks)
- Body composition. Resistance training can improve body composition even without weight loss. Body composition will therefore be assessed using dual-energy absorptiometry (DXA) using the enCORE Lunar iDXA software suite (GE Healthcare, Little Chalfont, UK). DXA provides a precise measure of fat mass, lean mass, total % body fat, and visceral fat and is sensitive to small changes from pre- to post-intervention.³⁰
 - **When collected:** Baseline, final visit (~10 weeks)
- Functional fitness. The functional fitness test (FFT) is a battery of six tests measuring strength, flexibility, fitness, body composition, and agility. It has high test-retest reliability and is suitable for tracking within-person changes.³¹ The functional fitness test battery includes the following 6 assessments: 1.) **The 30 second chair stand**, which assesses the strength of the lower body. Each person will have 30 seconds to stand up and sit down from a chair as many times as possible within the time frame. 2.) **The 30 second arm curl** assesses the strength of the upper body, where women will hold a 5 pound dumbbell in a seated position, and they will have 30

seconds to curl their arm and extend it as many times as possible within the time frame. 3.) The **6 minute walk test** measures the total distance that a person can quickly walk on a flat hard surface within a period of 6 minutes, using a 100ft length of distance. 4.) **The chair sit and reach** assesses the lower body flexibility where the participant will sit in a chair, extend one leg in front of them and flex at the waist, reaching toward their toes, and we will measure the distance between their toes and fingers. 5.) **The 8-foot-up and go** is an assessment of speed agility and balance. With this assessment, the participant begins in a seated position, and will be timed for the duration it takes to rise from the chair, walk as quickly as possible around a cone 8 feet away from the chair, and return to a seated position. 6.) **The back scratch test** is an assessment of the flexibility of the upper body, where the person will be seated and one arm will be flexed behind the head, and the other arm will be extended behind the shoulder. The assessment measures the distance between the finger tips of both hands.

- **When collected:** Baseline, final visit (~10 weeks)
- **Quality of life (QOL).** QOL changes will be captured using the Functional Assessment of Cancer Therapies (FACT) questionnaire including the Endometrial subscale (FACT-En).³² These measures will be repeated at the study mid-point (5 weeks) to assess changes over time.
 - **When collected:** Baseline, mid-point (~5 weeks), final visit (~10 weeks)
- **Mental well-being.** Changes in mental well-being (including anxiety, depression, and fatigue) will be assessed using standardized PROMIS measures.³³ These measures will be repeated at the study mid-point (5 weeks) to assess changes over time.
 - **When collected:** Baseline, mid-point (~5 weeks), final visit (~10 weeks)
- **Self-efficacy.** This will be assessed using the validated self-efficacy for exercise scale, modified for specificity to strength training.³⁴ These measures will be repeated at the study mid-point (5 weeks) to assess changes over time.
 - **When collected:** Baseline, mid-point (~5 weeks), final visit (~10 weeks)
- **Adherence.** Compliance and adherence will be measured via detailed exercise logs. A participant needs to complete at least 50% of the prescribed exercises in a session to be considered adherent to the session.
 - **When collected:** ongoing, logs will be completed throughout the intervention and submitted at the final visit
 - Additionally, for those in the intervention arm, we will ask that they continue to conduct the prescribed exercises for an additional five weeks after study completion. Participants will still submit paper logs, and this adherence measure will allow for study of adherence without prescribed check-ins from the study coordinator over the five week period.
- **Acceptability.** Participants will participate in a semi-structured qualitative interviews with the study coordinator. Interviews will be recorded, transcribed and coded to identify content themes. These interviews will be used to collect qualitative information and overall satisfaction with the intervention, as well as areas to improve with future interventions and barriers to participation.
 - **When collected:** Final visit (~10 weeks)

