6.4.3 Recruitment and Retention Strategies

Participants will be recruited primarily through referrals at the research site. If necessary, participants may be recruited through community partnerships through fliers and word of mouth recruiting.

Because the intervention is only 10 weeks in duration with a five week follow up, we do not anticipate major issues with participant retention. We have experience conducting several previous PA trials in cancer survivors and typically observe only ~5% loss to follow-up in a short-term study. To encourage retention, participants will receive \$50 compensation at the baseline visit and again at the 10-week follow-up visit.

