7.7 Early Withdrawal of Subjects

7.7.1 When and How to Withdraw Subjects

Participants may withdraw from the study prior to expected completion due to safety reason, losses to follow up, failure of subject to adhere to protocol requirements, subject consent withdrawal, etc.

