7.7.2 Data Collection and Follow-up for Withdrawn Subjects

Data will be attempted to be gathered from participants who have withdrawn from the study to collect their data prior to their withdrawal, including emails from the research staff and telephone calls.

Withdrawn subjects will be analyzed using an intent to treat analysis, therefore maximizing the amount of data is paramount to success. However, if participants cannot be contacted after 3 attempts from the study team (both telephone calls and emails) then the participants will be considered lost to follow-up.

8 Study Procedures

Wait list interventions

After being randomized to the wait-list group, participants will be scheduled for their 10 week follow up visit. The wait list arm will not have the additional five week follow up that the exercise arm receives. Participants will be reminded that at that final visit, participants will complete the same study measures (body composition, functional fitness testing, blood sample collection, and anthropometrics) and will also receive study materials at the end of their wait list period. Participants in the wait list group will also complete accelerometer (Actigraph) assessments at three study points: Early in the intervention near the instructional visit, at the mid-way (5-week) mark, and before the final visit. These accelerometers will be sent and received via mail and participants will receive instructions on how to wear, use and send to us during the instructional visit.

Exercise interventions

After being randomized to the exercise (intervention) arm, participants will be scheduled for an instructional visit with the study coordinator within a week of randomization. At that visit, participants will be instructed to wear comfortable clothes and shoes for learning the exercises. The instructional visit includes going through each exercise of the intervention (see Table below) to learn the movement, learn the muscle groups involved, and to learn how to monitor themselves by tracking their progress via logs. This instructional visit should take 60-90 minutes, and each participant will receive a summary sheet of her starting point at each exercise with respect to intensity and progressions/regressions. For example, a participant may be starting on a blue resistance band for biceps curls, but the squats may simply be body weight at this time. Table below outlines the exercises for the intervention.

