9.3 Subject Population(s) for Analysis

The populations for this investigation include:

- All-randomized population: Any subject randomized into the study, regardless of whether they received study agent
- All-treated population: Any subject randomized into the study that received at least the instructional visit of the intervention
- Protocol-compliant population: Any subject who was randomized, was allocated to the exercise group and provided at least one set of data elements required by the protocol.

9.3.1 Describe the types of analysis:

- **Primary Analysis:** The primary objective includes measuring the percentage of completed sessions compared to prescribed, and a one-sample t-test will be conducted to determine if that proportion, across participants, is >90%. A one-sample t-test will be done to determine if retention is >90%.

- **Secondary Analyses:** The secondary analyses includes measuring the objective and functional changes from pre to post intervention as well as differences between groups. Paired ANOVAs and descriptive statistics will be used to analyze functional and objective data, as well as participant feedback data, including satisfaction with each component of the intervention.
- **Exploratory, longitudinal analyses:** Content analysis will be done on the qualitative interviews to examine barriers to physical activity, as well as satisfaction with the intervention, and identification of themes to improve the intervention. Although formal hypothesis testing is not part of our specific aims, we will conduct longitudinal analyses of the data we collect to estimate potential magnitude of expected changes, as well as longitudinal analysis of the repeated measures.
- **Safety Analysis:** The safety analysis includes simple descriptive analysis about the number of adverse events over the course of the intervention between groups and across sites.

9.4 Planned Interim Analysis:

There are no planned interim analyses for this investigation.

10 Data Collection, Handling and Record Keeping

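### Adherence logs are handed in at the final visit and undocumented sessions have no score, so the primary adherence figure may be too high if women who drop out also exercised less

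*Combined protocol and SAP*

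**What the plan says.** Section 4.1.1 makes adherence to the prescribed sessions the primary endpoint, measured from exercise logs and video sessions. Section 9.3.1 analyses it by "measuring the percentage of completed sessions compared to prescribed" and tests the mean across participants against 90% with a one-sample t-test. Section 8 asks the exercise arm to "complete the exercise routine twice a week for 10 weeks during the intervention". Section 8.1 counts a session as adherent if at least half of its exercises are done.

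Two places describe how logs reach the study team. Section 8.1 says that "logs will be completed throughout the intervention and submitted at the final visit". Table 3 lists adherence logs as weekly, under a heading for additional data gathered while the intervention runs. Weekly could mean weekly pages, as in Appendix 3, or weekly collection; the heading leans towards collection.

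On withdrawal, Section 7.7.2 says "Withdrawn subjects will be analyzed using an intent to treat analysis" and has staff try to retrieve data from before withdrawal. Section 10.2.1 leaves the missing-data method to be chosen later with the biostatistician, and anticipates sensitivity analyses or model-based approaches.

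**The concern.** Handing in logs at the final visit ties the primary data to attendance at that visit. A woman who stops exercising and does not come back may contribute no log. Section 7.7.1 includes "failure of subject to adhere to protocol requirements" among the reasons for leaving, so loss of logs could be related to the endpoint itself. Section 14 names high attrition in the treatment group as a concern, though it rates it as less likely.

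No section gives a score for a session with no record. The video sessions in 4.1.1 are a second source, but no rule says how they combine with logs or replace a missing one. If the analyst averages over returned logs, the figure describes the women who stayed. With about 20 women in the arm, one or two can move the mean by several points, close to the 90% reference value.

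**Working it through.** **Inputs from the plan**
- 40 women randomised 1:1 (Sections 6 and 8.5), so about 20 in the exercise arm.
- Two sessions a week for 10 weeks, so 2 × 10 = 20 sessions per woman.
- Expected loss (Section 6.4.3): the team says it will "typically observe only ~5% loss to follow-up in a short-term study". 0.05 × 40 = 2 women; retention 38/40 = 95%, which still meets the Section 2.2 hypothesis that "we will meet the accrual goal and maintain >90% retention".

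The plan gives no expected adherence, SD, alpha or sidedness, so there is no adherence figure to reproduce.

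**Assumptions**
- Completer mean c = 95%.
- Lost women did L = 0, 20 or 40% of their 20 sessions.
- For the t-test: one-sided, completer SD 5 or 10 points.

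**Step 1. Mean over the whole arm with k women lost:** ((20 − k) × c + k × L) / 20.

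| k | L = 0% | L = 20% | L = 40% |
|---|---|---|---|
| 0 | 95.0% | 95.0% | 95.0% |
| 1 | 90.25% | 91.25% | 92.25% |
| 2 | 85.5% | 87.5% | 89.5% |

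The mean from returned logs is 95% in every cell. The overstatement is therefore 95 − 92.25 = 2.75 to 95 − 90.25 = 4.75 points with one lost, and 95 − 89.5 = 5.5 to 95 − 85.5 = 9.5 points with two. If L = c, it is 0.

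**Step 2. How many of the two expected losses fall in the exercise arm?** If loss is unrelated to arm:
- none: (20 × 19)/(40 × 39) = 380/1560 = 24%
- one: (2 × 20 × 20)/(40 × 39) = 800/1560 = 51%
- two: 380/1560 = 24%

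**Step 3. The planned test, one woman lost.**
- 19 completers only: t = 5 × √19 / SD. SD 5 gives t = 4.36, p = 0.0002; SD 10 gives t = 2.18, p = 0.021.
- All 20, lost woman at 0%: mean 90.25%. The SD rises to 21.8 (from 5) or 23.4 (from 10); t = 0.05 and p = 0.48 in both cases.
- All 20, lost woman at 40%: mean 92.25%. The SD rises to 13.2 or 15.7; t = 0.76 or 0.64, p = 0.23 or 0.26.

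Much of the change in p comes from one outlying value inflating the SD. The shift in the mean in Step 1 is the better measure of the problem.

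**The case against.** The best defence is that the plan leaves less open than it seems.

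**Denominator.** A reader might infer that it is undefined after withdrawal. Sections 7.7.2 and 9.3.1 do not support that: analysing withdrawn women by intent to treat, and comparing completed with prescribed sessions, together point to 20 sessions for every woman. This stands. What they do not supply is a score for sessions without a record.

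**Population.** Section 9.3 lists three populations and assigns none to the adherence analysis, so a reader might infer that the choice could change the result materially. It has little effect. Only exercise-arm women have sessions prescribed in the 10 weeks. Section 8.5 randomises after baseline measures are complete, so read literally every woman randomised to exercise already meets the data requirement of the protocol-compliant set. The all-treated set, those who "received at least the instructional visit of the intervention", drops only exercise-arm women who never attend that visit. This stands too.

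**Safeguards.** Section 7.7.2 tries to retrieve earlier data, Section 14 plans a support person and several contact details per woman, and the calls in Section 8 review the volume, intensity and difficulty of each exercise. These make a complete absence of records less likely. They do not say how any remaining gap is counted.

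**Descriptive purpose.** Sections 2.1, 9.1 and 9.2 disclaim hypothesis testing, and no go/no-go rule hangs on 90%. This limits the harm, but a descriptive estimate still needs a stated way to count undocumented sessions.

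**Conclusion.** The point holds as a minor to moderate weakness in how the primary endpoint is collected and scored. Section 8.1 and Table 3 need reconciling, and undocumented sessions need a score.

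Under the stated assumptions, one lost woman in the exercise arm means an overstatement of 2.75-4.75 points, with the arm mean still above 90%. Two mean 5.5-9.5 points, with the arm mean below 90%. With none lost there is no effect.

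A reader might go further and conclude that adherence will be overstated, or that the plan's expected attrition overturns the 90% result. The documents do not support either. They do not show that women who leave exercise less, the bias is zero if they adhered like completers, and the p-value reversal owes much to the effect of one outlier on the SD. What is at stake is an adherence estimate that may be too high when it is used to design the larger study.

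**What to change.** 1. **Section 8.1 and Table 3.** Replace hand-in at the final visit with collection during the 10 weeks: log pages by photo or e-mail from the supplied tablet, or recorded at the planned check-ins. The last check-in listed in Section 8.2 is in week 8, so take weeks 9-10 by photo, by e-mail or at the final visit. Word Table 3 to match.
2. **Section 9.3.1.** State that the primary adherence figure includes every woman randomised to exercise, withdrawn or lost included, over the 20 sessions of the 10-week period. Report the five-week follow-up separately.
3. **Section 9.3.1.** Name one primary figure in advance: sessions with no log or call record count as not done. Give the documented-only figure as a single sensitivity analysis, and list reasons for leaving.

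The cost is wording in three places and a small submission burden, using tablets and calls already planned. Sending pages in may itself prompt adherence, which should be acknowledged when the result is reported.

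Counting undocumented sessions as not done is conservative and debatable, because a mislaid log or a safety withdrawal then counts as non-adherence. With one woman of 20 at zero the arm mean cannot exceed 19/20 = 95%; with two it cannot exceed 18/20 = 90%, so more than 90% could not be shown. That is why the documented-only figure belongs beside it. Collecting pages as they are completed softens the effect: a woman who leaves after week 4 with all 8 sessions logged counts as 8/20 = 40%, not 0.
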